2.8.4 Other safety data

2.8.4.1 ECG and cardiac imaging data

Fridericia's formula (QTcF) will be used to calculate the heart rate-corrected QT interval (ms) based on the heart rate (HR bpm) and QT (ms) for centrally-read data. These calculated QTc values will be used in ECG summary tables and listings. The formula is as follows:

$$QTcF \text{ (in ms)} = QT / (RR)^{1/3}$$

The following analyses will be performed for variables PR, QRS, QT interval, heart rate, and QTcF (Fridericia's) for the overall study period:

- summary statistics at baseline, all post-baseline time points as well as corresponding change from baseline.

- For randomized withdrawal period: summary statistics at randomization, all time points within randomized withdrawal period as well as corresponding changes from randomization
- Listing of ECG data including all scheduled and unscheduled time points

No imputation of missing data will be performed.

The number and percentage of patients with notable ECG interval values will be summarized.

A newly occurring ECG finding is defined as an notable finding at post-baseline that is not present at baseline.

The notable criteria for PR are

- > 200 ms post-baseline and \leq 200 ms at baseline
- Increase > 25% compared to baseline to a post-baseline value > 200 ms

The notable criteria for QRS are

- > 110 ms post-baseline and \leq 110 ms at baseline
- Increase > 25% compared to baseline to a post-baseline value > 110 ms

The notable criteria for QT and QTcF are

- > 450 ms at any post-baseline and \leq 450 ms at baseline
- > 480 ms at any post-baseline and \leq 480 ms at baseline
- > 500 ms at any post-baseline and \leq 500 ms at baseline
- an increase from baseline > 30 ms at any post-baseline
- an increase from baseline > 60 ms at any post-baseline

The percentage of patients having notable ECG interval values is based on the total number of patients who are at risk for a specific category. For new abnormality post-baseline values, this is the number of patients with both baseline and post-baseline evaluations who are normal at baseline. For abnormal change from baseline, this is the number of patients with both baseline and post baseline evaluations. A subject with multiple occurrences of a newly occurring abnormality is counted only once per abnormality.

All ECG data will be listed. If corrected QTcF are provided (providing them is optional), they will be listed in addition to the values derived using the formulae above. (In the summaries only the derived values will be used.) The patients with notable ECG interval values will be listed and the corresponding notable values will be flagged in the listings.

For 24hr Holter assessment, summaries of the key parameters will be provided. The worst observed post-baseline value for each patient, for each parameter will be presented.

The following parameters will be presented using shift tables

- % of patients with maximum HR >100 bpm
- % of patients with minimum HR <40 bpm
- % of patients with average HR >90 bpm

- % of patients with total SVEs >200
- % of patients with total VEs >200

The following parameters will be presented as change from baseline

- Total number of pauses >2 seconds
- Total SVE run events
- Total VE run events

To ensure accurate reporting of results, only Holter assessments which were performed for at least 20 hours will be used in any analysis.

All 24hr summary results will also be listed for the reported assessments.

2.8.4.2 Vital signs

All vital signs data (weight (kg), body temperature ($^{\circ}$ C), pulse rate (beats per minute), and systolic/diastolic blood pressure (mmHg)) will be listed by patient and visit/time, and abnormalities will be flagged on listing. Shift table based on notable value will be provided for vital signs. For blood pressure, triplicate measurements are planned when assessed, and the mean of available values will be taken for analysis purposes. Change over time from baseline will be summarized.

The criteria for clinically notable abnormalities are defined as follows:

Clinically notable elevated values

- Systolic BP: ≥ 180 mmHg and an increase ≥ 20 mmHg from baseline
- Diastolic BP: ≥ 105 mmHg and an increase ≥ 15 mmHg from baseline.
- Pulse: ≥ 120 bpm with increase from baseline ≥ 15 bpm
- Weight: Increase from baseline of $\geq 10\%$
- Temperature: Increase from baseline of $\geq 39.1^{\circ}$ C

Clinically notable below normal values

- Systolic BP: ≤ 90 mmHg and a decrease ≥ 20 mmHg from baseline
- Diastolic BP: ≤ 50 mmHg and a decrease ≥ 15 mmHg from baseline
- Pulse: ≤ 50 bpm with decrease from baseline ≥ 15 bpm
- Weight: Decrease from baseline of $\geq 5\%$

2.8.4.3 Tumor volume

For tumor volume evaluated by MRI (or CT) scanning in patients with detectable tumor volume at baseline, descriptive summary of actual tumor volumes as well as its change from baseline will be provided at visits where evaluation is scheduled (Week 24, 48, 72 and any further visits

occurring every 24 weeks). For MRI (or CT) images that are not interpretable for tumor volume, the longest dimension (in mm) will be listed instead.

Tumor invasiveness at each scheduled visit, and the change in status from baseline will be reported.

The proportion of patients with measurable tumors at each visit, and the change in status from baseline will be reported.

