7.1.4 End of treatment visit including study completion and premature withdrawal

Patients who discontinue study treatment before visit 777 (if patient is in the core phase of the study) or 778 (if patient is in the extension phase of the study), should be scheduled for a visit as soon as possible, at which time all of the assessments listed for the EOT visit will be performed ([Table 7-1](#), [Table 7-3](#) or [Table 7-5](#)) with the following exceptions:

- Patients discontinuing treatment prior to the Week 36 visit do not need to have an EOT core DXA scan

- Patients discontinuing prior to the Week 12 visit or between the Week 24 and Week 36 visits do not need to have an EOT core pituitary MRI (or CT) (i.e. scans are needed if patients discontinue within the 12 week period prior to the Week 24 and Week 48 visits).
- Patients discontinuing or completing extension phase within 36 weeks since their last pituitary MRI (or CT) or DXA scan do not need to have an EOT extension pituitary MRI (or CT) or DXA scans.

An End of Treatment Phase Disposition CRF page should be completed, giving the date and reason for stopping the study treatment. At a minimum, all patients who discontinue study treatment, including those who refuse to return for a final visit, will be contacted for safety evaluations during the 30 days following the last dose of study treatment (Visit 779).

If a patient withdraws or discontinues from the study prematurely, an unscheduled PK sample should be taken, and the sample should be recorded in the “Unscheduled PK” CRF page.

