7.1.5 Discontinuation of study treatment

Patients may voluntarily discontinue from the study treatment for any reason at any time. If a patient decides to discontinue from the study treatment, the investigator must make every effort (e.g. telephone, e-mail, letter) to determine the primary reason for this decision and record this information in the patient’s chart and on the appropriate CRF pages. They may be considered withdrawn if they state an intention to withdraw, fail to return for visits, or become lost to follow-up for any other reason.

- The investigator should discontinue study treatment for a given patient if, on balance, he/she believes that continuation would be detrimental to the patient’s well-being.

Study treatment must be discontinued under the following circumstances:

- Emergence of the following adverse events:
 - hypertension defined as office mean sitting systolic BP > 180 mmHg or mean sitting diastolic BP > 110 mmHg (confirmed and persistent*).
- Any of the following laboratory abnormalities (confirmed):
 - hyperkalemia (serum potassium > 6.0 mmol/L).
 - hypokalemia (serum potassium < 2.8 mmol/L).
- Any of the following laboratory abnormalities (confirmed and persistent*):
 - hyperkalemia (serum potassium > 5.5 mmol/L).
 - hypokalemia (serum potassium < 3.0 mmol/L).
 - hyponatremia (serum sodium < 130 mmol/L).
 - AST or ALT >3.0 x ULN combined with total bilirubin >2.0 x ULN without evidence of cholestasis
- QTcF > 500 msec, if confirmed by a cardiologist (see [Section 7.2.2.7](#)).

QTcF > 480 msec, if the investigator determines it is no longer safe for the patient to continue in the study, based on ECGs, cardiac examination, and recommendation from a cardiologist (see [Section 7.2.2.7](#)).

- QTcF increase > 60 msec from pre-first dose baseline measurement.

- Mean increase in QTcF > 30 ms from the mean baseline value at 1.5 hour post-first dose or mean QTcF > 480 ms at day 1 (see [Section 7.2.2.7](#)).
- Pituitary tumor growth, if the tumor is < 2mm from the optic chiasm, or symptoms of actual compression of the optic chiasm emerge (visual field loss, cranial nerve palsies, diplopia) confirmed by MRI of the pituitary.

* Persistent is defined as unresolved with LCI699 dose and/or other concomitant medication changes.

- Pregnancy.
- Use of prohibited concomitant medications (see [Section 6.4.2](#)).
- Any other protocol deviation that results in a significant risk to the patient's safety.

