7.2.2.5 Radiological examinations

Table 7-8 Imaging assessment collection plan

Procedure	Screening/Baseline	During Treatment/Extension
Pituitary MRI with gadolinium enhancement	Mandated at baseline	Mandated at Week 24, 48,72, 120, subsequently at the same frequency and at EOT extension

Pituitary MRI scanning with gadolinium enhancement will be performed at visits according to [Table 7-1](#) to [Table 7-5](#). These will be assessed centrally by the imaging vendor to screen for pituitary enlargement either by tumor volume or maximum dimension of tumor. If MRI scan

with intravenous contrast (gadolinium) is contraindicated for a patient, then a non-contrast MRI scan should be performed. If the MRI cannot be performed at all, then a CT of the pituitary (with i.v. contrast if not contraindicated) may be performed. Regardless of imaging type, all regularly scheduled pituitary imaging will be centrally reviewed by the imaging vendor for consistency in the measurement of dimensions. The modality (MRI/CT) should remain consistent to that used at baseline unless there is a development of a contraindication. The central reading at each time point will include the assessment of invasiveness of the pituitary tumor into surrounding structures, and any new finding of measurable pituitary tumor in a patient with no measurable tumor at previous scans. Please see the study imaging manual for further information.

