10.5.3.4 Other safety data

ECG

ECG data will be summarized with

- shift table baseline to worst on-treatment result for overall assessments
- Number and percentage of patients with clinically notable QT/QTcF interval values will be summarized.
- listing of ECG evaluations for all patients with at least one abnormality.

Vital signs

Vital signs (supine BP, HR & temperature) reporting of results will include

- shift table baseline to worst on-treatment result
- table with descriptive statistics at baseline, one or several post-baseline time points and change from baseline to this/these post-baseline time points.

Tumor volume

For tumor volume evaluated by MRI (or CT) scanning, descriptive summary of actual tumor volumes as well as its actual and percent change from baseline will be provided. The number and percentage of patients with newly occurring measurable tumor and/or new evidence of tumor invasion into surrounding structures during the study will be calculated. For MRI (or CT) images that are not interpretable for tumor volume, the longest dimension (in mm) will be summarized instead.

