2.1.1.3 Visit number

The time point (Day/Month) associated with an assessment will be determined by the visit number assigned to the assessment in the database. The mapping of visit numbers to time points in the core study and the extension study are provided in the table below.

Table 2-1 Scheduled visits in core phase

Core study Visit	Day/Week	Clarifying Notes
Visit 1	Day -35 to Day -8	Screening
Visit 2	Day -7 to Day -1	Baseline
Visit 3	Day 1/Week 0	Dose escalation period
Visit 4	Day 15/Week 2	Dose escalation period
Visit 5	Day 29/Week 4	Dose escalation period
Visit 6	Day 43/Week 6	Dose escalation period
Visit 7	Day 57/Week 8	Dose escalation period
Visit 8	Day 71/Week 10	Dose escalation period
Visit 9	Day 85/Week 12	Dose escalation period
Visit 10	Day 113/Week 16	Treatment period
Visit 11	Day 141/Week 20	Treatment period
Visit 12	Day 169/Week 24	Treatment period
Visit 13	Day 183/Week 26	Randomized Withdrawal period
Visit 14	Day 197/Week 28	Randomized withdrawal period
Visit 15	Day 211/Week 30	Randomized withdrawal period
Visit 16	Day 225/Week 32	Randomized withdrawal period
Visit 17	Day 239/Week 34	Randomized withdrawal period

Core study Visit	Day/Week	Clarifying Notes
Visit 1	Day -35 to Day -8	Screening
Visit 18	Day 253/Week 36	Open Label period
Visit 19	Day 281/Week 40	Open Label period
Visit 20	Day 309/Week 44	Open Label period

Table 2-2 Scheduled visits in extension period

Extension study Visit	Day/Week	Clarifying Notes
Visit 21	Day 337/Week 48	Extension
Visit 22	Day 365/Week 52	Extension
Visit 23	Day 393/Week 56	Extension
Visit 24	Day 421/Week 60	Extension
Visit 25	Day 449/Week 64	Extension
Visit 26	Day 477/Week 68	Extension
Visit 27	Day 505/Week 72	Extension
Visit 28	Day 589/Week 84	Extension
Visit 29	Day 673/Week 96	Extension
Visit 30	Day 757/Week 108	Extension
Visit 31	Day 841/Week 120	Extension
.....	Every 84 days/12 weeks	Extension

Unlike the above visits that are scheduled to occur after a fixed number of days have elapsed since Day 1, the Visits 777 (End-of-Treatment in core phase) and 778 (End-of-Treatment in extension period) are scheduled when the patient either completes the respective study period or decides (or is mandated by the protocol) to prematurely discontinue from the study.

If such a visit happens neither too soon nor too late after the actual last scheduled visit (LASTVIS) prior to the 777/778 visit, then it will be mapped to the next scheduled visit (LASTVIS+1) in the visit schedule (from the tables above).

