The 777/778 visit will be considered to have occurred neither too soon nor too late after the actual last scheduled visit if the number of days between the two visits is

- (i) at least half of the planned gap between the patient’s actual last scheduled visit (LASTVIS) and the next scheduled visit and
- (ii) at most the total of (a) the planned gap between the patient’s actual last scheduled visit (LASTVIS) and the next scheduled visit and (b) half of the planned gap between the patient’s next two scheduled visits.

If the number of days between the 777/778 visit and LASTVIS is less than the range specified above then the 777/778 visit will be mapped to an unscheduled visit of LASTVIS; if it is more then it will be mapped to an unscheduled visit of LASTVIS + 1.

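### The SAP's tumor-volume table has no end-of-treatment or last-available row and omits the protocol's whole-study count of new tumor or invasion, so it may miss growth first seen off schedule

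*SAP*

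**What the plan says.** **Protocol.** Table 7-8 (section 7.2.2.5) sets the pituitary MRI schedule: "Mandated at Week 24, 48,72, 120, subsequently at the same frequency and at EOT extension". For early stops in the core phase, section 7.1.4 explains that "scans are needed if patients discontinue within the 12 week period prior to the Week 24 and Week 48 visits". In the extension it waives the EOT scan if the last one was within 36 weeks. Section 7.1.5 makes "Pituitary tumor growth, if the tumor is < 2mm from the optic chiasm" a reason to stop treatment, and section 8.1.3 lists pituitary tumor enlargement among the adverse events of special interest (AESIs). Section 10.5.3.4 plans actual volumes with actual and percent change, a summary of longest dimension where volume cannot be read, and the number and percentage of "patients with newly occurring measurable tumor and/or new evidence of tumor invasion into surrounding structures during the study".

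**SAP.** Section 2.8.4.3 restricts the volume summary to patients with detectable tumor volume at baseline and to the weeks in "provided at visits where evaluation is scheduled (Week 24, 48, 72 and any further visits", those further visits being 24 weeks apart. Percent change is not mentioned. Longest dimension is listed, not summarized. Invasiveness is reported at each scheduled visit and measurable tumor at each visit, both with change in status from baseline. Section 2.1.1.3 reassigns the EOT visits (777 in the core, 778 in the extension). If the timing is within a window, "then it will be mapped to the next scheduled visit (LASTVIS+1) in the visit schedule". If the interval is "less than the range specified above then the 777/778 visit will be mapped to an unscheduled visit of LASTVIS". If it is too long, the visit becomes an unscheduled visit attached to the next scheduled one. Section 4, for changes to protocol-specified analyses, has no entry.

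**The concern.** Growth close to the optic chiasm is a reason to stop treatment, so the timing of a patient's last scan can depend on the outcome being measured. A table confined to fixed weeks describes patients who were scanned at those weeks. Growth first seen on an early EOT scan or an unscheduled scan has no row to enter, and later rows describe patients still on treatment.

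The protocol's whole-study count would have picked up new tumor and new invasion whatever the scan date. It matters most for patients with no detectable tumor at baseline, because the SAP's volume table excludes them altogether.

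Other measures in the same SAP keep late or worst values. Bone mineral density has a last available assessment, photography has EOT extension, laboratory data have worst and last values, Holter has the worst value, and QTcF counts any post-baseline exceedance. Tumor volume has none of these.

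**Working it through.** The plan gives no figure to reproduce here. The check is to apply the SAP mapping rule to each last visit after which the protocol requires an EOT scan.

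**Inputs.** Visit days come from SAP Tables 2-1 and 2-2. The scan requirement comes from protocol 7.1.4. Visit 778 is nominally 28 days after the last visit (protocol Table 7-5). The SAP volume weeks are 24, 48, 72, 96, 120, 144, 168 and so on.

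**Rule (SAP 2.1.1.3).** Let g1 be the planned gap from the last visit to the next scheduled visit, and g2 the gap after that. The EOT visit takes the next scheduled week if it falls between g1/2 and g1 + g2/2 days after the last visit. Otherwise it is unscheduled.

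**Core phase (scan required for stops in Weeks 12–24 and 36–48).**

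| Last visit | g1, g2 (days) | Window (days) | Maps to | Volume week? |
|---|---|---|---|---|
| Week 12 | 28, 28 | 14–42 | Week 16 | No |
| Week 16 | 28, 28 | 14–42 | Week 20 | No |
| Week 20 | 28, 14 | 14–35 | Week 24 | Yes |
| Week 36 | 28, 28 | 14–42 | Week 40 | No |
| Week 40 | 28, 28 | 14–42 | Week 44 | No |
| Week 44 | 28, 28 | 14–42 | Week 48 | Yes |

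Four of the six last visits lead to a week that is not in the volume table. The two that are kept include the patients who complete Week 48. An EOT visit less than 14 days after any of these visits becomes unscheduled and has no row.

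**Extension.** At the nominal 28 days (4 weeks), the time since the last scheduled scan is:
- last visit Week 96: 96 + 4 − 72 = 28 weeks, so no scan is required;
- last visit Week 108: 108 + 4 − 72 = 40 weeks, so a scan is required;
- last visit Week 156: 156 + 4 − 120 = 40 weeks, so a scan is required.

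After Week 72 visits are 84 days apart, so the window runs from 84/2 = 42 days to 84 + 42 = 126 days. At 28 days the EOT visit is below 42 and becomes unscheduled. Between 42 and 126 days it maps to Week 120 or Week 168, both of which are volume weeks, and is kept.

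**Schedule after Week 72.** The SAP's 24-week step gives Weeks 96, 120, 144 and 168. The protocol goes from Week 72 to Week 120, a step of 48 weeks, and then continues at the same frequency, which gives Week 168. Protocol Tables 7-4 and 7-5 show no MRI at Week 96 or Week 144. The two schedules do not agree, but the SAP grid contains the protocol weeks, so this mismatch by itself loses no scan.

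**The case against.** A reader might infer that all EOT scans drop out and that tumor progression is therefore understated. The documents do not support that.

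- **Part of the EOT scans are kept**, as the mapping shows. Growth seen on a scheduled scan also stays in that week's row, even if the patient then stops.
- **The risk is reported elsewhere.** SAP 2.8.1.4 tabulates AESIs overall, those leading to discontinuation and those requiring dose adjustment or interruption. SAP 2.8.1.6 shows AESIs by time of onset, and SAP 2.3.1 gives the reasons for discontinuation. SAP 2.1.1.9 says that all data are at least listed and that safety data other than adverse events and deaths will be summarized.
- **New tumor is partly retained**, because measurable tumor is reported at each visit and not only at scheduled ones.
- **This SAP serves the final report.** The core phase was analysed under a separate SAP dated 06-Jul-2018, which is not available here and may have included the whole-study count.

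These points remove any claim of demonstrated bias, but they do not close the gap. AESI tables depend on an event being reported and coded, and they give no volume change. The secondary safety objective names pituitary MRI as a source in its own right beside investigator reports. A listing is not a summary. The general statement in 2.1.1.9 names no table, while 2.8.4.3 is specific and limits the weeks. A core report cannot supply a count that runs through the extension.

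One caution stands: protocol 7.2.2.5 promises central review only for regularly scheduled imaging, so some unscheduled scans may have no central volume.

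**Conclusion.** The concern holds in a limited form. The volume table may miss growth first seen off schedule, because it has no last-available or EOT row and a definable part of the required EOT scans, plus unscheduled scans, falls outside its weeks. Separately, this SAP leaves out the protocol's whole-study count of new measurable tumor or invasion, drops percent change and downgrades longest dimension from summary to listing, without recording any of these in section 4.

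The size cannot be computed. The documents give no number of off-schedule scans and no tumor changes, and four of six core last visits is a count of visits, not of patients. The direction of any effect is not established either. The finding rests on reading 2.8.4.3 as limiting the volume summary to the weeks it names, and on the nominal 28-day timing of the extension EOT visit. It is an inexpensive improvement to a safety summary and does not affect the primary or key secondary analysis.

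**What to change.** In SAP 2.8.4.3:

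1. Add actual and percent change in tumor volume from baseline to the last available scan on LCI699, using all central reads, including visits 777 and 778 and any unscheduled scan that was centrally read.
2. Restore the number and percentage of patients with new measurable tumor and/or new invasion at any time during the study, as in protocol 10.5.3.4.
3. Summarize longest dimension where volume is unreadable.
4. Reconcile the 24-week step after Week 72 with the protocol's MRI schedule.
5. Record any remaining departure from the protocol in SAP section 4.

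A maximum post-baseline change per patient is optional. It selects measurement noise upward and tends to grow with the number of scans, so it should not replace the last-available row.

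The cost is SAP wording and one extra table, from scans that the protocol already collects. The tumor result may look slightly less favourable.

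### For scans that cannot be read for tumor volume, the SAP lists the longest dimension where the protocol summarizes it, so the Final CSR's size-change summary leaves those scans out

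*SAP*

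**What the plan says.** Protocol section 10.5.3.4 sets the analysis of tumor size. For volume, "descriptive summary of actual tumor volumes as well as its actual and percent change from baseline will be provided". For scans that do not yield a volume there is a fallback: "For MRI (or CT) images that are not interpretable for tumor volume, the longest dimension (in mm) will be summarized instead".

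SAP section 2.8.4.3 keeps the volume summary, restricted to patients who had a detectable volume at baseline: "descriptive summary of actual tumor volumes as well as its change from baseline will be provided at visits where evaluation is scheduled". It repeats the fallback sentence almost word for word but changes the verb: "the longest dimension (in mm) will be listed instead". It then adds two status outputs: "Tumor invasiveness at each scheduled visit, and the change in status from baseline will be reported", and "The proportion of patients with measurable tumors at each visit, and the change in status from baseline will be reported".

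Protocol section 7.2.2.5 describes the central reading, which is meant to "screen for pituitary enlargement either by tumor volume or maximum dimension of tumor". Dimension is therefore a planned measure of growth in its own right.

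SAP section 4, where departures from the protocol's analyses would be declared, has a heading and no text in the supplied copy.

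**The concern.** A listing and a summary do different jobs. A listing shows individual values. It gives no count, no mean or median, and no change from baseline by visit. With dimension moved to a listing, the report's statistics on tumor size rest on volume-readable scans alone.

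The subject is a safety question that the trial takes seriously. Protocol section 2.7 names corticotroph tumor progression as a potential risk, section 8.1.3 makes pituitary tumor enlargement an adverse event group of special interest, and section 7.1.5 includes tumor growth near the optic chiasm among the reasons for stopping treatment. This SAP governs the Final CSR, which covers the extension as well as the core phase, so the long-term size data are reported under its rule.

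**Working it through.** The point depends on no sample size, power or event figure, so there is nothing to recompute. The check sets the two texts side by side and follows the SAP rule through each case.

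**Comparison**

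| Item | Protocol 10.5.3.4 | SAP 2.8.4.3 |
|---|---|---|
| Volume | Summary with actual and percent change | Summary with change from baseline; percent change not named |
| Scan without a readable volume | "the longest dimension (in mm) will be summarized instead" | "the longest dimension (in mm) will be listed instead" |
| Departure declared in SAP section 4 | n/a | None in the supplied text |

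Both are current text; neither comes from an amendment summary.

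**What the SAP rule does in each case**

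1. *Baseline and later scan both readable for volume.* The patient contributes a volume change at that visit. Nothing is lost.
2. *Baseline readable for volume, a later scan readable only by dimension.* The volume change is missing at that visit and the dimension goes to the listing. The patient still contributes at other readable visits.
3. *Baseline readable only by dimension.* There is no baseline volume to subtract, so there is no volume change at any visit, even if later scans are readable for volume.
4. *No measurable tumor at baseline.* There is no baseline size by either measure. The measurable-tumor output is the relevant one, and the listed-or-summarized question does not arise for change from baseline.

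The loss falls in cases 2 and 3. In case 2 it is per visit. It is complete in case 3, and also in case 2 when no later scan is readable for volume.

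**Whether another SAP output fills the gap**

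The invasiveness and measurable-tumor outputs are categorical. A measurable, non-invasive tumor that grows but stays non-invasive changes neither status. The special-interest adverse event tables (SAP sections 2.8.1.4 and 2.8.1.6) count reported events, not measured size. None of these gives a size change.

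**Whether such scans are foreseen**

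They are, because both documents carry a fallback sentence for them. How often they occur is not stated anywhere.

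**The case against.** The strongest reply is that little is lost. It has several parts, and most of them stand in part.

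- *The patients are still reported.* This stands. Each dimension is listed, and these patients can appear in the invasiveness, measurable-tumor and special-interest outputs. The rule also works per image. A reader might infer that such patients drop out of tumor safety reporting altogether; the documents do not support that. What is missing is a summarized size change for those scans.
- *The number affected is unknown.* This stands. A reader might be tempted to apply an assumed share of unreadable scans to all 137 treated patients. No share is given, and 137 is not the right base, because the SAP summary is limited to patients with a detectable baseline volume and inclusion criterion 3 allows the pituitary source to be confirmed by petrosal sinus sampling or histopathology instead of an MRI finding.
- *The omitted scans need not differ from the rest.* A reader might infer that they are a selected group, such as small remnants, CT or non-contrast images. Criterion 3 admits tumors of 6 mm or less and section 7.2.2.5 permits those modalities, so this is possible, but no text says that such scans are unreadable for volume.
- *The core-phase analysis may already contain the summary.* This is possible. The SAP dated 06-Jul-2018 was not supplied, and protocol section 10 says its methods focus on the core study, with similar methods in the extension as appropriate. A core-phase summary to Week 48 would still leave the later extension visits uncovered.
- *The blank section 4 may be an extraction loss.* This is also possible, so the point rests on the verb conflict and not on the blank section.
- *With few scans, a listing tells more than a by-visit mean over a changing subset.* This is reasonable, but it is a reason to state in the SAP.

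**Conclusion.** The inconsistency is real. The protocol promises a summary of the longest dimension for scans without a readable volume, and the SAP provides only a listing, with no reason in the supplied text. Followed as written, the Final CSR's one descriptive summary of size change omits those scans. It has no entry for any patient who lacks a volume-readable scan at both baseline and a later visit.

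The size of the effect cannot be given from the documents. It could be negligible if nearly all scans are readable for volume. No hypothesis test or efficacy conclusion depends on this table, and stopping for tumor growth is decided patient by patient. The point still deserves correction because it weakens, without explanation, a planned safety summary on a named risk.

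A reader might also infer that the protocol promises change from baseline for dimension. It does not say so explicitly: the change statistics are attached to volume, and dimension is only to be summarized. Nor does any text confirm that dimension was recorded on scans that were readable for volume. Both limits carry into the fix.

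**What to change.** In SAP section 2.8.4.3, change *listed* to *summarized* and keep the listing as well. Specify one descriptive table by visit with:

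- the longest dimension (mm) for scans that cannot be read for volume;
- its within-patient change from baseline, only where a dimension is available at both time points;
- the number of patients contributing by volume, by dimension and by neither.

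If too few scans qualify for a useful table, report their number and record the departure and its reason in SAP section 4.

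The cost is one added table. The dimension values are already destined for the listing, so the by-visit summary needs no new reading. The change from baseline for patients whose baseline was read by volume depends on whether a dimension was also recorded then, which should be checked with the imaging vendor's data before the table shell is fixed.
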